15. RISK MANAGEMENT PROCEDURES AND ADEQUACY OF RESOURCES

SERIOUS ADVERSE EVENT REPORTING

Serious Adverse Events

Serious adverse events will be collected throughout the study period, beginning with the signing of the informed consent through seven days post the last tape stripping. Serious adverse events also will be collected if they occur > 30 days after the end of the study and is thought to be possibly related to investigational product.

An adverse event is any undesirable sign, symptom, or medical condition occurring after starting the study drug (or therapy). Medical conditions / diseases present before starting the study treatment are only considered adverse events if they worsen after starting study treatment.

A serious adverse event is defined by regulatory agencies as one that suggests a significant hazard or adverse event, regardless of the investigator or sponsor's opinion on the relationship to investigational product. This includes, but may not be limited to, any event that (at any dose):

- is fatal
- is life threatening (places the subject at immediate risk of death)
- requires in-patient hospitalization or prolongation of existing hospitalization
- results in persistent or significant disability/incapacity
- constitutes a congenital anomaly/birth defect
- is medically significant, in that it may jeopardize the subject and may require medical or surgical intervention to prevent one of the outcomes listed above.

Any event that does not exactly meet this definition, but in the investigator's opinion represents a significant hazard (eg, emergency room visit or outpatient surgery), can be assigned the "other significant hazard" in regards to reporting serious criteria.

Additionally, important medical events that may not be immediately life threatening or result in death or hospitalization but that may jeopardize the subject or require intervention to prevent one of the outcomes listed above, or result in urgent investigation, may be considered serious. Examples include allergic bronchospasm, convulsions, and blood dyscrasias.

Reporting Procedures for All Adverse Events

The investigator is responsible for ensuring that all adverse events are properly recorded in the subjects' records. After signing of the informed consent form, all adverse events observed by the investigator or reported by the subject (whether or not attributed to investigational product), will be recorded in the case report form.

The following attributes must be assigned by the investigator: description; dates of onset and resolution; severity; assessment of relatedness to investigational product, and action taken. The investigator may need to provide follow-up information, medical records, and extracts from medical records.

Adverse Events Standard Grading Score

Clinical investigators will “grade” the severity of all AEs using the following scale; the results will be reported on the SAE form, if necessary.

1 = MILD – aware of sign or symptom, but easily tolerated

2 = MODERATE – discomfort enough to cause interference with usual activity

3 = SEVERE – incapacitating with inability to work or do usual activity

4 = LIFE-THREATENING – refers to an event in which the patient was, in the view of the investigator, at risk of death at the time of the event. It does not refer to an event which hypothetically might have caused death if it were more severe.

5 = FATAL

Recording and Reporting Obligations for SAEs

The investigator will provide the IRB appropriate information concerning any findings that suggest there has been an SAE related to the study. Any adverse event that is considered serious must be reported within one working day by the investigator to Galderma and to the IRB as required.

The investigator will notify the UCSD Human Research Protections Program of any unexpected, fatal or life-threatening experiences in writing no later than 10 working days of the event, according to standard IRB procedures. All serious and medically significant adverse events considered related to the product by the investigator will be followed until resolved or considered stable.

Unexpected and related fatal or life-threatening events will be reported to FDA by phone or FAX within 7-calendar day.

A written report will be sent to FDA within 15 calendar days for any serious unexpected adverse event considered related to study drug (including those which have already been reported under the 7 day rule).

Additionally, any pregnancies reported during this study will be reported to Galderma.

Withdrawal from Medications: Adverse events associated with stopping the use of protocol-prohibited medications may result in worsening of the condition being treated.

Irritation from tape strips: It is possible but unlikely that patient's may have some irritation due to the application of tape strips. Patient will be instructed to inform study doctor if irritation occurs.

Irritation from skin swabs: It is possible but unlikely that patient's may have some irritation due to the skin swabs. Patient will be instructed to inform study doctor if irritation persists.

Confidentiality: Subject confidentiality will be maintained by the investigator, the investigator's associates and co-workers, and by all administrators who are part of the ADVN project. Confidentiality will be maintained according to ICH E6; 4.8.10, part O: “Records identifying the subject will be kept confidential and, to the extent permitted by the applicable laws and/or regulations, will not be made publicly available. If the results of the trial are published, the subject's identity will remain confidential.”

Treatment and Monitoring: If a subject has experienced an adverse event from use of topical Ivermectin or otherwise, the subject will be asked to return to the site. Actions taken in response to an AE will be recorded in the subject's medical record in accordance with the site's procedures. Any treatment administered for the AE

must be recorded in the subject's source document.

All subjects will receive verbal and written instructions with site contact information for whom to contact if they experience an AE associated with study procedures performed for this protocol or if the subject resumes their protocol-prohibited medication during the washout period.

Medically significant adverse events considered related to the study by the investigator will be followed until resolved or considered stable.

It will be left to the investigator's clinical judgment whether or not an adverse event is related and of sufficient severity to require the subject's removal from treatment. A subject may also voluntarily withdraw from treatment due to what he or she perceives as an intolerable adverse event. If either of these occur, the subject must undergo an end-of-study assessment and be given appropriate care under medical supervision until symptoms cease or the condition becomes stable. If the subject was permanently withdrawn from the study or investigational product due to a serious adverse event, this information must be included in either the initial or follow-up Serious Adverse Event Report Form.

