9. RESEARCH DESIGN AND METHODS

This trial is designed as a pilot study to determine the range and mechanism of monitoring biochemical surrogates of rosacea after daily topical Ivermectin 1% cream treatment. This is a single-site 16-week open label study at University of California, San Diego. Up to 25 subjects (age 18+) with at least one inflammatory papule (IGA>1) and at least mild erythema (see Clinical Assessment for Inclusion Criteria) will all be treated with topical ivermectin daily for up to 12 weeks with 4 in-office visits (screening, then monthly follow-ups for 3 months and one follow-up telephone visit one month after study medication completion). Twenty tape strip samples (similar to the tape strip method described in Dyjack, et. al. 2018) from each of the four sites will be obtained at each visit to determine KLK activity and LL-37 expression and/or up to twelve skin swabs to assess skin microbiome. Safety monitoring has been established based on both the most likely reactions and the most serious though extremely rare events. At each visit, in addition to one planned phone call, the subject will be queried tolerance of therapy and Adverse Events. The study will end with the last subject completing the telephone visit (Visit 5/week 16). If a patient does not return for a follow up visit after baseline, a replacement patient will be added.

The biochemical analysis of protease activity and LL-37 cathelicidin expression obtained by tape strip analysis at each time point and compared to baseline. Analysis of the tape strips will compare baseline to week 12 and also be correlated to the trends assessed in the tape strip analysis. The skin microbiome obtained by skin swab will also be analyzed at each time point and compared to baseline.

Ivermectin 1% cream is lawfully marketed in the U.S. as a topical treatment for inflammatory lesions of rosacea. Subjects will be instructed on the proper application of Ivermectin topical cream in accordance with the package insert, and they will apply a pea-sized amount for each area of the face that is affected daily. This research proposal therefore does not involve a route of administration, dose, or patient population that significantly affects the risk to benefit ratio associated with the use of the drug product.
Furthermore, this is a proof of concept study, and therefore, this investigation is not intended to support a

change in advertising of the drug, in labeling, nor in promoting the drug product.

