On Visit 3, rosacea severity will again be evaluated. Tape strips and/or skin swabs will be collected from the same sites as in the initial collection. Patients will be instructed not to apply the study drug on the morning before the tape strip samples are collected on return visits. Study drug will be weighed, and additional drug will be provided as needed. The total time for this visit will be approximately 1 hour.

VISIT 4 Week 12 (+/- 4 days)

On Visit 4, rosacea severity will again be evaluated. Tape strips and/or skin swabs will be collected from the same sites as in the initial collection. Patients will be instructed not to apply the study drug on the morning before the tape strip samples are collected on return visits. Study drug will be weighed, and additional drug will be provided as needed. The total time for this visit will be approximately 1 hour.

Visit 5 Week 16 (+/- 4 days) (phone follow-up)

Subjects will be contacted via phone to inquire about any adverse events experienced since the last in clinic visit. This phone call will take approximately 5 minutes.

Clinical assessments for inclusionary criteria:

IGA scale, a subjective 5-point measure of overall disease severity. IGA scores range from 0 to 4: 0 = no signs or symptoms present (clear); 1 = 1 to 2 small, noninflammatory papules (near clear); 2 = 3 to 10 papules/pustules (mild); 3 = 11 to 19 papules/ pustules (moderate); and 4 = 20 or more papules/pustules and nodules (severe).

Erythema scale: Scores range from 0-4: 0=none (no redness present); 1= mild (slight pinkness); 2= moderate (definite redness); 3=significant (marked erythema); and 4=severe (fiery redness). For inclusion criteria subjects will require at least mild erythema.

Lesional site identification and sample collection:

At Visit 1, Four ~20x20mm areas will be identified as clinically involved. These sites will be recorded to ensure subsequent sampling is from the same area during follow up visits (Visits 2-4).

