All information required will be entered into the Case Report Forms (CRFs). The objective of this trial is to determine if 12 weeks of topical ivermectin to affected areas of facial skin can decrease biochemical markers of rosacea-specific inflammation and affect the skin microbiome. Changes in lab measures before and after treatment will be compared pre and post Ivermectin treatment using paired sample t-tests. Variables with right-skewed distributions will be log transformed at each time (pre and post treatment) before analysis. If log transformations do not provide distributions suitable for 2-sample t-tests (based on violation to the normality assumption), the Wilcoxon Rank-Sum test will be employed.

Sample Size Calculation

Given this is a proof of concept study, no sample size calculation will be performed.

Safety Data

All AEs, including SAEs, occurring during the course of this study will be listed for all subjects. Adverse events resulting in discontinuation from the study will be listed separately. Other information collected about AEs (e.g., severity or relationship to study procedures) will be listed as appropriate.

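### The post-study window for serious adverse events leaves out the first 30 days after study end, and the in-study window disagrees with the week-16 follow-up

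*Combined protocol and SAP*

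**What the plan says.** Two consecutive sentences in Section 15, under Serious Adverse Events, set dated windows for SAE collection.

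- The first opens by promising collection for the whole study, then limits it to the period "beginning with the signing of the informed consent through seven days post the last tape stripping".
- The second adds a post-study rule for events thought possibly related to the product: "Serious adverse events also will be collected if they occur > 30 days after the end of the study".

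Section 9 sets the follow-up that these windows should match.

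- On enquiry: "At each visit, in addition to one planned phone call, the subject will be queried tolerance of therapy and Adverse Events".
- On the week-16 call: "Subjects will be contacted via phone to inquire about any adverse events experienced since the last in clinic visit".
- On the end of the study: "The study will end with the last subject completing the telephone visit (Visit 5/week 16".
- On the safety listing, under Safety Data: "All AEs, including SAEs, occurring during the course of this study will be listed for all subjects".

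Two further rules in Section 15 carry no end date. Under Reporting Procedures for All Adverse Events, every event observed or reported after consent goes into the case report form. Under Recording and Reporting Obligations for SAEs, any serious event must be reported within one working day.

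**The concern.** The main problem is the second sentence. A post-study rule normally picks up where in-study collection stops. This one starts only after 30 days have passed, and the sentence before it supplies no 30-day period for it to extend. The stated windows therefore include later possibly related events and omit the earliest ones. The study's end is also a trial-level date, fixed by the last subject, so the omitted stretch is longer for everyone who finishes before that subject.

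The lesser problem is the first sentence. It ties the end of SAE collection to a sampling procedure, while Section 9 goes on asking about adverse events until week 16. Two parts of one document then give different answers for an SAE in the last weeks of follow-up.

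What is at stake is clear and complete safety capture. No endpoint or efficacy analysis depends on it.

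**Working it through.** The documents give rules and not day numbers, so there is no stated figure to reproduce. The days below are calendar arithmetic.

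**Inputs**
- Last scheduled tape stripping: Visit 4, week 12, ±4 days (Section 9, Table of Events and visit descriptions).
- Stop of the first SAE window: last tape stripping plus 7 days (Section 15).
- Last scheduled contact: Visit 5, the week-16 call, ±4 days (Section 9).
- Study end: the last subject's week-16 call (Section 9).
- Start of the post-study window: more than 30 days after study end (Section 15).

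**Post-study window (main point)**
- Nominal study end for the last subject: 16 × 7 = day 112.
- More than 30 days after that leaves out 112 + 1 = day 113 to 112 + 30 = day 142, which is 30 days. The window opens on day 143.
- For a subject whose own last contact falls d days before study end, the time after that contact and before the second window opens is d + 30 days. For the last subject d = 0, so 30 days is the minimum for anyone who completes the week-16 call.
- The documents give no enrolment dates, so d cannot be calculated. As a ceiling only, assume that the two-year duration estimated in Section 4 runs from the first subject's baseline to study end. Then d for that subject is at most about 104 − 16 = 88 weeks.

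**In-study window (secondary point)**
- Nominal stop: 12 × 7 + 7 = 84 + 7 = day 91.
- Week-16 call: day 112. The rules disagree for 112 − 91 = 21 days (days 92 to 112).
- Shortest, with a late Visit 4 and an early call: (112 − 4) − (84 + 4 + 7) = 108 − 95 = 13 days.
- Longest, with an early Visit 4 and a late call: (112 + 4) − (84 − 4 + 7) = 116 − 87 = 29 days.
- Day 91 assumes tape stripping at week 12. The visit descriptions allow tape strips, swabs or both, although the Table of Events marks both at every clinic visit. If the last tape strips were taken at week 8, the window would close on 56 + 7 = day 63, and the disagreement would be 112 − 63 = 49 days.

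**Which other rules reach each period**
- Days 92 to 112: the week-16 call asks about everything since the last clinic visit, the case report form rule has no end date, the one-working-day rule has no end date, and the safety listing covers the course of the study.
- After a subject's week-16 call: no contact is scheduled. Only the undated recording and reporting rules remain, and they depend on an event being observed or volunteered.

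**The case against.** The strongest reply is that an inclusive reading already works. The first sentence does begin by covering the whole study. The week-16 call actively asks about events, all events after consent are recorded, and serious ones are reported within one working day, all without a stop date. A reader might infer that SAE collection really ceases on day 91 and that events on days 92 to 112 would go unrecorded. The documents do not support that. For this part the objection stands: it is an inconsistency in wording, and the period is probably covered.

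The reply is weaker for the post-study period. The undated rules might still bring in an event that a subject volunteers, so it would also be too strong to say that such events will be lost. But nobody is due to ask, and the one sentence written for this period leaves out its first 30 days. The threshold may well be a drafting slip. Even so, the text as it stands sets the window, and the neighbouring sentence does not repair it.

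It is also fair to say that little is likely to happen in practice. The drug is marketed, up to 25 subjects are planned, and Section 9 describes the most serious events as extremely rare. That limits the weight of the point but not its accuracy.

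**Conclusion.** The SAE windows in Section 15 are wrong as written and should be corrected; the consequence is modest.

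- The substantive error is the post-study window. It omits 30 days after study end (nominal days 113 to 142 for the last subject), plus, for each earlier finisher, the time from that subject's last contact to study end. It is a gap in the stated window, not a demonstrated loss of data.
- The secondary point is a contradiction over 21 nominal days within the study (13 to 29 with the visit windows). It would be longer if tape stripping stopped before week 12.

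A reader might add 21 and 30 and report 51 uncovered days. That sum should not be used: the first figure is a disagreement between rules over days that are probably covered, and the second is a gap in a stated window.

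The figures assume nominal visit days and, for day 91, tape stripping at week 12. The text and arithmetic are certain. How many events would be affected cannot be estimated from the documents and is probably few.

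**What to change.** Reconcile the two Section 15 sentences with the visit schedule, end-of-study definition and safety listing in Section 9, and with the SAE reporting obligations later in Section 15. Define the windows per subject and make them contiguous:

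- Run the first window from consent to each subject's last study contact: the week-16 call, the end-of-study assessment that Section 15 already requires for subjects taken off treatment for an adverse event, or the last contact for anyone else who withdraws or is lost. Drop the tape-stripping anchor.
- Start the window for possibly related SAEs immediately after that contact, with no gap before or after study end. Closing only the first 30 days after study end would not be enough, because the interval between an earlier finisher's last contact and study end would stay open.

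The cost is protocol wording and possibly a few more events to record. The call and the end-of-study assessment already exist, no visit is added, and no endpoint or analysis changes.

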Table of Events

Visit number	Screening /Baseline Visit 1*	2	3	4	5 (Phone Visit)
Time of Visit	Day -31 to Day 0	Week 4	Week 8	Week 12	Week 16
Demographic Information	x				
Inclusion/Exclusion criteria	x				
Informed consent	x				
Physical examination	x				
Rosacea Severity Score (IGA & CEA)	x	x	x	x	
Medical History	x				
Subject Satisfaction Assessment					
Tape strip	x	x	x	x	
Skin swabs	X	X	X	X	
Weigh/dispense study medication as needed	x	x	x	x	
Weigh and return study medication		x	x	x	
Adverse events	x	x	x	x	x

*Patients who require washout may be re-screened

VISIT 1 (Day 0)

Prior to beginning any study procedures, subjects will first be asked to review and sign the informed consent form. After obtaining informed consent, the inclusion/exclusion criteria will be reviewed. A brief medical history and physical exam will be performed in helping to assess whether the subject meets the required criteria for the study. Female subjects of child-bearing potential will complete a urine pregnancy test while in our office to ensure that they are not pregnant. Patients who meet the inclusion and exclusion criteria will then have their rosacea severity scored by two different standardized grading scales: IGA and erythema scale. At the screening visit may occur at the same time as your screening visit if none of your medications are excluded. Tape strips and/or skin swabs will be collected from 4 areas of involved rosacea facial skin. Subjects will then be given a pre-weighed tube of study medication and instructed to apply the medication daily. Subjects will also be instructed not to apply the study drug on the morning before the tape strip samples are collected on return visits. The total time for this visit will be approximately 1 hour.

VISIT 2 Week 4 (+/- 4 days)

On Visit 2, rosacea severity will again be evaluated. Tape strips and/or skin swabs will be collected from the same sites as in the initial collection. Patients will be instructed not to apply the study drug on the morning before the tape strip samples are collected on return visits. Study drug will be weighed, and additional drug will be provided as needed. The total time for this visit will be approximately 1 hour.

VISIT 3 Week 8 (+/- 4 days)

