10. HUMAN SUBJECTS

Up to 25 adult subjects (age 18+) will be enrolled with a diagnosis of rosacea and at least mild erythema and one inflammatory papule. The specific criteria for subjects will be discussed below. Each subject must be capable of providing informed consent.

Inclusion:

- Subject is male or non-pregnant female, 18+years of age.
- Subjects willing and able to give informed consent.
- Subjects willing and able to comply with the requirements of the study.
- Subject has the clinical diagnosis of rosacea with at least one inflammatory papule and at least mild erythema.
- Subject has been on a stable dose for greater than 3 months of medications for treatment of concurrent medical condition (including oral contraceptive pills, vasodilators, adrenergic blocking agents) OR the investigator has determined that the medications are unlikely to affect the patient's rosacea and/or treatment during the study
- Subject is in general good health in the opinion of the investigator.
- .
- Exclusion: Subject has a diagnosis of Steroid Rosacea or Pyoderma Faciale (rosacea fulminans).
- Subject has used facial topical therapies (OTC drug products or prescription products) for any reason within the prior 7 days
- Subject has used oral ivermectin within the prior 28 days.
- Subject has used systemic corticosteroid or systemic antibiotics (especially doxycycline, minocycline, tetracycline, metronidazole) within the prior 28 days.
- Subject has had laser or light-based treatment for rosacea within the prior 3 months.
- Subject has had systemic retinoids and retinoid derivatives over the past 6 months
- Subject has a known hypersensitivity or allergy to topical ivermectin or components of the vehicle.
- Subject is pregnant or lactating or planning a pregnancy during the duration of the study
- Subject has been treated with another investigational device or drug within 28 days prior to study enrollment or intends to participate in a clinical trial concurrent with this study
- Subject has clinically significant findings, medical history or conditions (other than rosacea), which in the opinion of the Investigator may compromise the study, treatment protocol, or safety of the patient or treatment allocation

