Although this drug was approved by the FDA for the treatment of rosacea, it does carry some risks. Hypersensitivity to topical ivermectin cream or any components of the cream is possible. Also, the study sponsor reports that the medication may cause sensations of burning/stinging/redness/itching at local sites of application. There have also been rare reports of burning, dry, itching eyes as well as redness, pain, excessive tearing or discharge, swelling of the eye if contact occurs with the eyes. This research plan does not utilize a route, dose, or patient population that differs from its lawfully marketed purpose.

Topical Ivermectin Pregnancy Category: C

There are no adequate and well-controlled studies in pregnant women.

Effect on lactation: Following oral administration, ivermectin is excreted in human milk in low concentrations; excretion following topical administration has not been evaluated

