19. EXPENSE TO PARTICIPANT

The participant is not expected to incur any expenses. Since there are no lab draws or biopsies associated with this study aside from a pregnancy test for females of child-bearing potential, which we will do in our outpatient dermatology clinic, there will not be any study-related charges to either the patient or his/her insurance.

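### After the single urine test at Visit 1, no later contact asks about pregnancy, so the reporting duty covers only pregnancies that a subject happens to mention

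*Combined protocol and SAP*

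**What the plan says.** Section 10 (Human Subjects) makes pregnancy a bar to entry twice. An inclusion criterion reads "Subject is male or non-pregnant female, 18+years of age", and an exclusion criterion reads "Subject is pregnant or lactating or planning a pregnancy during the duration of the study". Section 14 (Potential Risks) gives the background: the product is in pregnancy category C, and "There are no adequate and well-controlled studies in pregnant women".

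The check is in the Visit 1 text of section 9 (Research Design and Methods): "Female subjects of child-bearing potential will complete a urine pregnancy test while in our office to ensure that they are not pregnant". Section 19 (Expense to Participant) mentions the same test in passing ("aside from a pregnancy test for females of child-bearing potential, which we will do in our outpatient dermatology clinic"), with no visit and no repeat. The Table of Events has rows for consent, eligibility criteria, physical examination and medical history, but none for a pregnancy test.

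For later contacts, section 9 provides for questions on tolerance and adverse events at each visit and at the Week 16 call. The text for Weeks 4, 8 and 12 each says: "Study drug will be weighed, and additional drug will be provided as needed". The table likewise marks dispensing at all four clinic visits.

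The one sentence about a pregnancy arising during the study is in section 15, at the end of the reporting obligations for serious adverse events: "Additionally, any pregnancies reported during this study will be reported to Galderma".

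**The concern.** The exclusion looks forward. It covers women planning a pregnancy during the study, so the authors had pregnancy under treatment in mind as well as status on the day of entry. Section 15 also expects that pregnancies may occur. Yet nothing between the Visit 1 test and that reporting sentence would bring a pregnancy to light unless the subject volunteers it.

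Two things are at stake. One is subject safety: a woman who conceives after Visit 1 could attend a clinic visit and receive more cream without anyone having asked. The other is complete reporting: a duty that covers only reported pregnancies is only as good as the means of learning about them. The comparison of protease activity, LL-37 and microbiome before and after treatment is not at stake.

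**Working it through.** The plan gives no figure on this point, so there is nothing to reproduce. The check sets the relevant parts of the protocol side by side and counts.

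| Contact | Pregnancy test or question | Other questions provided for | Drug may be supplied |
|---|---|---|---|
| Visit 1 (Day -31 to Day 0) | Urine test, in the visit text only | Adverse events, eligibility, history | Yes |
| Visit 2 (Week 4) | None | Tolerance, adverse events | Yes |
| Visit 3 (Week 8) | None | Tolerance, adverse events | Yes |
| Visit 4 (Week 12) | None | Tolerance, adverse events | Yes, by both text and table |
| Visit 5 (Week 16, phone) | None | Tolerance, adverse events | No |

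**Counts.** There is 1 scheduled test, 0 pregnancy-test rows in the Table of Events, 0 pregnancy questions at the 4 later contacts, and 3 later visits at which drug may be supplied.

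**Interval without a check.** Treatment lasts 12 weeks, 12 × 7 = 84 days. The Week 12 visit has a window of plus or minus 4 days. The table allows Visit 1 from Day -31 to Day 0.
- Test on Day 0: 84 + 4 = 88 days at most to the end of the Week 12 window.
- Test on Day -31: 31 + 84 + 4 = 119 days at most.

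The second figure assumes that the urine test is done at the early edge of the window and not repeated when treatment starts. The protocol schedules no repeat.

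**Would the adverse-event query pick it up?** Section 15 defines an adverse event as an undesirable sign, symptom or medical condition arising after the drug is started, and it does not name pregnancy. A subject asked about adverse events might mention a pregnancy, but nothing requires it. Removal from treatment is described in section 15 only in relation to adverse events. The instructions given to subjects there concern adverse events and resumption of prohibited medication.

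**What reaches the IRB?** A congenital anomaly or birth defect is a listed criterion for a serious adverse event, and such events go to Galderma and, as required, to the IRB. That covers an outcome. The pregnancy sentence itself names Galderma alone. Routine collection of serious adverse events ends seven days after the last tape stripping; later events are collected when they occur more than 30 days after the end of the study and are thought possibly related to the product.

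**The case against.** The best reply is that the protocol can be followed as it stands. Section 10 sets entry criteria, the Visit 1 text checks one of them at entry, the later visit texts describe supply, and section 15 says what to do with a pregnancy that is reported. The product is marketed and used by its labelled route, at its labelled dose and in its labelled population. Subjects are seen or telephoned at about four-week intervals, and each contact is an occasion on which a pregnancy could come up.

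Much of this stands, and it rules out several stronger readings that a reader might infer:

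- *The protocol contradicts itself on whether the exclusion continues after entry.* It does not. No section addresses the question, and silence is not disagreement.
- *The entry test is likely to be missed because the table omits it.* The documents do not say that staff work from the table alone. The table has an eligibility-criteria row at Visit 1, those criteria require non-pregnancy, and the Visit 1 text states the test. The missing row is a minor misalignment.
- *Nothing about pregnancy can reach the IRB.* Birth defects can, as serious adverse events.
- *Subjects are told nothing about pregnancy during the study.* Section 12 refers to an attached consent form, which was not available for this review. It may contain such instructions.

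What survives is narrower. A general adverse-event query is not a pregnancy question, the serious-adverse-event route covers an outcome and not the pregnancy, and section 15 depends on a report that nothing in the supplied text elicits.

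**Conclusion.** The point holds as a minor safety and reporting gap. There is one check at entry, then four contacts with no question about pregnancy, three of which allow re-supply. The longest interval without a check is 88 to 119 days, depending on when in the Visit 1 window the test is done. The only stated action is a report to Galderma, and only for pregnancies that come to light unprompted.

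The intervals describe the schedule and do not measure risk. The documents do not say how many of the up to 25 subjects will be women of child-bearing potential, so no expected number of pregnancies can be given. The conclusion rests on the protocol text as supplied, without the consent form. No statistical result depends on it.

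**What to change.** 1. Add a pregnancy-status question, for women of child-bearing potential, to the adverse-event query already made at Visits 2 to 5. This is the change that closes the gap.
2. Add the Visit 1 urine test to the Table of Events so that the table agrees with the Visit 1 text and with section 19.
3. Reconcile the Visit 1 to 4 texts and Table of Events in section 9, the criteria in section 10 and the pregnancy sentence in section 15, so that the protocol states how a pregnancy during the study is handled and to whom it is reported, including whether the IRB is told. What a pregnancy means for treatment and re-supply is a clinical rule for the investigator to set; none is proposed here.

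The cost is one extra question at each of four existing contacts, at most 25 × 4 = 100 questions if every subject were eligible to be asked, plus one table row and a few sentences of protocol wording. No visit, sample or procedure is added.
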